2.2.1. Thigh PK Sub-study Objectives and Endpoints

[figure not shown]
| Objectives | Endpoints |
|---|---|
| Primary Objectives | Primary Endpoints |
| 
 To evaluate the PK of monthly and every two months dosing of CAB LA and RPV LA injections following intramuscular administration in the vastus lateralis (thigh) muscle (compared to gluteal injections) in HIV-1 infected participants currently enrolled in the A2M sub-study | 
 Plasma PK parameters for CAB LA and RPV LA (C_{tau}, concentrations post dose [~C_{max}], and area under the curve [AUC (0-τ)]) for thigh injections during the thigh injection phase compared with similar PK parameters for gluteal injections. |
| 
 To assess safety and tolerability of monthly and every two months dosing of CAB LA and RPV LA following intramuscular injections in the vastus lateralis (thigh) muscle in HIV-1 infected participants currently enrolled in the A2M sub-study. To assess the ability to maintain virologic suppression (HIV-RNA < 50 copies/mL) in subjects who transition to thigh administrations of CAB and | 
 Incidence and severity of ISRs and AEs of special interest during the thigh injection phase. Proportion of participants who discontinue treatment due to ISRs and AEs of special interest during the thigh injection phase. Proportion of participants with plasma HIV-1 RNA <50 c/mL over time (including at Week 16) during the thigh injection phase using the FDA Snapshot algorithm. Proportion of participants with plasma HIV-RNA \geq50 c/mL over time (including at Week 16) as per Food and Drug |

| Objectives | Endpoints |
|---|---|
| RPV after receiving at least 3 years of gluteal injections. | 
Administration (FDA) Snapshot algorithm during the thigh injection phase.
 
 Proportion of participants with protocol-defined confirmed virologic failure (CVF) during the thigh injection phase. |

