8.2. Adverse Events of Special Interest Analyses

Adverse events of special interest (AESI) are determined for CAB and/or RPV based on pre-clinical and clinical experience, along with information for the Integrase Inhibitor class of HIV medications and RPV safety profile. [Table 4](#) shows the currently identified AESI, drug(s) of Interest and the reasons for inclusion. Changes to the MedDRA dictionary may occur between the start of the study and the time of reporting, and/or

emerging data from on-going studies may highlight additional adverse events of special interest, therefore the list of AESIs may change at the time of reporting.

A summary by system organ class and preferred term will be provided for each of AESI. The characteristics of event occurrences will be summarized in main study for common AESI which have at least 20 participants in either treatment arm, and will be summarized in sub-study for common AESI which have at least five participants in either treatment arm. For Depression, anxiety and suicidal ideation/behaviour AESI, a summary by system organ class, maximum DAVIDS toxicity grade and prior history of suicidal ideation will be provided. The details of the planned grouping and planned displays are provided in Section 15.11 and Appendix 15: List of Data Displays.

Table 4 Adverse Events of Special Interest

| Adverse Events of Special Interest | Drug(s) of Interest | Reason for Inclusion |
|--|---------------------|--|
| Hepatic Safety Profile: Assessment of Risk of hepatotoxicity | CAB+RPV | Clinical, Class, Regulatory Interest, More prevalent in HIV population |
| Hypersensitivity Reactions (HSR) | CAB | Class, Regulatory Interest, Occurs in HIV population |
| Rash | RPV | Class, Regulatory Interest, Occurs in HIV population |
| Prolongation of the Corrected QT Interval of the ECG in Supratherapeutic Doses | RPV | Non-clinical, Clinical, Regulatory Interest |
| Suicidal Ideation/Behaviour | CAB+RPV | Clinical, Class, Regulatory Interest, More prevalent in HIV population |
| Depression | CAB+RPV | Clinical, Class, Regulatory Interest, More prevalent in HIV population |
| Bipolar Disorder | CAB+RPV | Clinical, Class, Regulatory Interest, More prevalent in HIV population |
| Psychosis | CAB+RPV | Clinical, Class, Regulatory Interest, More prevalent in HIV population |
| Mood Disorders | CAB+RPV | Clinical, Class, Regulatory Interest |
| Anxiety | CAB+RPV | Clinical, Class, Regulatory Interest |

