15.11. Appendix 11: Identification of Adverse Events of Special Interest

The adverse events of special interest are identified based on MedDRA coded values and/or AE data available in the study database. The system organ classes (SOCs), preferred terms (PTs) or codes, Standardised MedDRA Queries (SMQs), High Level Group Terms (HLGTs), and High Level Terms (HLTs) below are from MedDRA 21.1. SMQs use narrow terms unless otherwise specified. In case there is a change to the version of MedDRA at time of reporting, the coded values based on the MedDRA version at the time of reporting will be used. The additional events may also be added based on the blinded review of AE data collected on study prior to the database freeze.

1. Hepatic Safety Profile: Assessment of risk of hepatotoxicity

Hepatic failure, fibrosis and cirrhosis and other liver damage-related conditions (SMQ)

| PT | PT Code |
|--------------------------------------|----------|
| Acquired hepatocerebral degeneration | 10080860 |
| Acute hepatic failure | 10000804 |
| Acute on chronic liver failure | 10077305 |
| Acute yellow liver atrophy | 10070815 |
| Ascites | 10003445 |
| Asterixis | 10003547 |
| Bacterascites | 10068547 |
| Biliary cirrhosis | 10004659 |
| Biliary fibrosis | 10004664 |
| Cholestatic liver injury | 10067969 |
| Chronic hepatic failure | 10057573 |
| Coma hepatic | 10010075 |
| Cryptogenic cirrhosis | 10063075 |
| Diabetic hepatopathy | 10071265 |
| Drug-induced liver injury | 10072268 |
| Duodenal varices | 10051010 |
| Gallbladder varices | 10072319 |
| Gastric variceal injection | 10076237 |
| Gastric variceal ligation | 10076238 |
| Gastric varices | 10051012 |
| Gastric varices haemorrhage | 10057572 |
| Hepatectomy | 10061997 |
| Hepatic atrophy | 10019637 |
| Hepatic calcification | 10065274 |
| Hepatic cirrhosis | 10019641 |
| Hepatic encephalopathy | 10019660 |
| Hepatic encephalopathy prophylaxis | 10066599 |

| PT | PT Code |
|--------------------------------------|----------|
| Hepatic failure | 10019663 |
| Hepatic fibrosis | 10019668 |
| Hepatic hydrothorax | 10067365 |
| Hepatic infiltration eosinophilic | 10064668 |
| Hepatic lesion | 10061998 |
| Hepatic necrosis | 10019692 |
| Hepatic steato-fibrosis | 10077215 |
| Hepatic steatosis | 10019708 |
| Hepatitis fulminant | 10019772 |
| Hepatobiliary disease | 10062000 |
| Hepatocellular foamy cell syndrome | 10053244 |
| Hepatocellular injury | 10019837 |
| Hepatopulmonary syndrome | 10052274 |

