| Radiation hepatitis | 10051015 |
| Steatohepatitis | 10076331 |

2. Hypersensitivity Reactions (HSR)

Drug reaction with eosinophilia and systemic symptoms syndrome (SMQ)

| PT | PT Code |
|---|----------|
| Drug reaction with eosinophilia and systemic symptoms | 10073508 |
| Pseudolymphoma | 10037127 |

PTs (Selective)

| PT | PT Code |
|-----------------------------------|----------|
| Drug hypersensitivity | 10013700 |
| Hypersensitivity | 10020751 |
| Type IV Hypersensitivity reaction | 10053613 |
| Eosinophilia | 10014950 |
| Eye swelling | 10015967 |
| Eyelid oedema | 10015993 |
| Lip swelling | 10024570 |
| Angioedema | 10002424 |
| Circumoral oedema | 10052250 |
| Face oedema | 10016029 |
| Idiopathic angioedema | 10073257 |
| Lip oedema | 10024558 |
| Mouth swelling | 10075203 |
| Oedema mouth | 10030110 |
| Periorbital oedema | 10034545 |
| Swelling face | 10042682 |
| Periorbital swelling | 10056647 |
| Swelling of eyelid | 10042690 |

3. Rash

Severe cutaneous adverse reactions (SMQ)

| PT | PT Code |
|---|----------|
| Acute generalised exanthematous pustulosis | 10048799 |
| Cutaneous vasculitis | 10011686 |
| Dermatitis bullous | 10012441 |
| Dermatitis exfoliative | 10012455 |
| Dermatitis exfoliative generalised | 10012456 |
| Drug reaction with eosinophilia and systemic symptoms | 10073508 |

| PT | PT Code |
|-----------------------------|----------|
| Epidermal necrosis | 10059284 |
| Erythema multiforme | 10015218 |
| Exfoliative rash | 10064579 |
| Oculomucocutaneous syndrome | 10030081 |
| Skin necrosis | 10040893 |
| Stevens-Johnson syndrome | 10042033 |
| Toxic epidermal necrolysis | 10044223 |
| Toxic skin eruption | 10057970 |

PTs (Selective)

| PT | PT Code |
|----------------------|----------|
| Eyelid rash | 10074620 |
| Genital rash | 10018175 |
| Mucocutaneous rash | 10056671 |
| Nodular rash | 10075807 |
| Perineal rash | 10075364 |
| Rash | 10037844 |
| Rash erythematous | 10037855 |
| Rash generalised | 10037858 |
| Rash macular | 10037867 |
| Rash maculo-papular | 10037868 |
| Rash maculovesicular | 10050004 |
| Rash morbilliform | 10037870 |
| Rash papular | 10037876 |
| Rash rubelliform | 10057984 |
| Rash scarlatiniform | 10037890 |
| Rash vesicular | 10037898 |
| Rash pruritic | 10037884 |
| Rash follicular | 10037857 |
| Rash pustular | 10037888 |
| Drug eruption | 10013687 |

4. Prolongation of the Corrected QT Interval of the ECG in Supratherapeutic Doses

Torsade de pointes/QT prolongation (SMQ)

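### The Hypersensitivity Reactions AESI counts angioedema and facial swelling but has no anaphylactic or Type I hypersensitivity term

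*SAP*

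**What the plan says.** SAP section 8.2, Table 4, names hypersensitivity as an AESI for cabotegravir: "Hypersensitivity Reactions (HSR) | CAB | Class, Regulatory Interest, Occurs in HIV population". The same section says "A summary by system organ class and preferred term will be provided for each of AESI", and the terms behind each AESI are fixed in Appendix 11 (section 15.11).

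Item 2 of that appendix builds the AESI from two parts:

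- The standardised query "Drug reaction with eosinophilia and systemic symptoms syndrome (SMQ", with two preferred terms. The appendix states the default scope: "SMQs use narrow terms unless otherwise specified".
- A selective list of 18 preferred terms. It holds drug hypersensitivity, hypersensitivity, "Type IV Hypersensitivity reaction", eosinophilia, and a run of swelling and oedema terms of the face, mouth, lips and eyes. One entry is "Angioedema | 10002424".

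The appendix leaves room for additions: "The additional events may also be added based on the blinded review of AE data collected on study prior to the database freeze". Section 8.2 likewise says that the AESI list may change at reporting. Neither place names a term.

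For the thigh sub-study, section 2.2.1 makes AESIs part of an endpoint: "Incidence and severity of ISRs and AEs of special interest during the thigh injection phase". A companion endpoint counts discontinuations due to the same events.

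**The concern.** The AESI carries a general title, and its contents show that immediate-type presentations are meant to be in scope: hypersensitivity without a type, angioedema, and swelling of the lip, mouth and face. A list confined to delayed or DRESS-type reactions would have been a defensible narrow definition, but this is not one. The only hypersensitivity term with a type is Type IV. Under the list as fixed, isolated eyelid oedema or eosinophilia counts as a hypersensitivity reaction, while an event coded as an anaphylactic reaction after an injection does not. The SAP gives no reason for the difference.

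At stake is whether the hypersensitivity table means what its title says. Read alone, it could show no events in an arm in which an anaphylactic reaction was reported. In the sub-study the same gap carries into an endpoint built on the AESI definition.

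**Working it through.** The SAP gives no figure to reproduce here. The check is a comparison of lists, with one division for scale.

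**1. Hypersensitivity list (Appendix 11, item 2).** DRESS query 2 + selected terms 18 = 20 preferred terms. A text search for the stems anaphyl, type i hyper, urticar, shock and bronchospasm gives 0 matches for each.

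**2. Rash list (Appendix 11, item 3).** Severe cutaneous query 14 + selected terms 20 = 34 preferred terms. The same search gives 0 matches.

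**3. Injection site reactions (Appendix 11, item 12).** This AESI takes the non-serious injection-site-reaction form, plus serious events whose reported term names the study drug injection site. A systemic reaction reported as such does not enter by this route.

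**4. Remaining AESI lists.** On reading, none contains an anaphylactic or Type I term. Item 13 (seizures and seizure-like events) includes syncope and loss of consciousness. A separately coded symptom could therefore be counted there, but not as hypersensitivity.

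**5. What the list does and does not count.**

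| Event as coded | Counted in the hypersensitivity AESI? |
|---|---|
| Eyelid oedema alone | Yes |
| Eosinophilia alone | Yes |
| Angioedema | Yes |
| Hypersensitivity or drug hypersensitivity | Yes |
| Type IV hypersensitivity | Yes |
| Type I hypersensitivity | No |
| Anaphylactic reaction | No |

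**6. Where the event would still appear.** The sub-study display list (section 15.15.7.4) has tables of all AEs by system organ class and maximum toxicity (Table 3.6), drug-related AEs (3.11), SAEs (3.14) and AEs leading to discontinuation (3.17). Section 15.15.7.10 has the matching listings. The Week 48, 96, 152 and End-of-Study lists have equivalent displays.

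**7. Scale in the sub-study.** Section 2.3 plans about 82 participants, 41 per arm. The AESI tables are produced one category at a time (section 15.15.7.4, Tables 3.49 to 3.66), so one assumed event omitted from one arm changes that arm's hypersensitivity incidence by 1/41 = 0.0244, or 2.4 percentage points. This is the effect of one hypothetical event, not an expected number.

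**8. Status of the sub-study endpoint.** In section 2.2.1 the safety endpoint stands under the Primary heading, and no Secondary heading appears before the Exploratory one. SAP section 7.2.1 lists the sub-study virologic endpoints from the same table among the secondary efficacy endpoints. The Primary label is therefore not secure for everything beneath it. Non-AESI adverse events and SAEs stand under the Exploratory heading.

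**The case against.** The strongest reply is that no safety information is lost. An event coded as an anaphylactic reaction is tabulated and listed elsewhere, and main-study safety endpoints cover all AEs. Neither section 8.2 nor Appendix 11 attaches a test, stopping rule or threshold to the hypersensitivity count. This stands. It limits the consequence to which table and which endpoint carry the event, but does not make the AESI table right under its own title.

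Second, the SAP provides a route to add terms before database freeze. That also stands as a description, and it means the event need not be missed in practice. But the clause is permissive and names no term. It also relies on blinded review in a trial that section 2.3 describes as open-label. A term that can be foreseen is better fixed in advance.

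Third, some reactions would be captured anyway, coded as hypersensitivity, drug hypersensitivity or angioedema. True: only an event coded solely to an unlisted term misses the hypersensitivity AESI. Capture then depends on the coding choice.

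Fourth, the content of an AESI is a medical definition, based on experience that the SAP does not reproduce. This is a fair caution, and it is why urticaria is left to the medical team. The case for anaphylactic and Type I terms is narrower, because it rests on what the list already includes.

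A reader might also infer that the omission changes a primary endpoint result. The documents do not support that firmly, because section 7.2.1 treats other endpoints from the same table as secondary. Nor do they support an inference that 2.4 points is a likely error, or that pooled AESI incidence moves by that amount. The figure assumes one event and applies to one table.

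**Conclusion.** The gap holds as a defect of definition. The pre-specified Hypersensitivity Reactions AESI covers immediate-type swelling and Type IV hypersensitivity but has no anaphylactic or Type I term among its 20, and no other AESI list supplies one. An event coded only to such a term would be absent from the hypersensitivity table and from the sub-study endpoint on incidence and severity of AESIs, while still appearing in the general AE displays and, if serious, the SAE displays.

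The practical size is small: few events would be affected, no inference depends on the count, and one assumed case is 2.4 percentage points of one sub-study arm in one table. The conclusion assumes that the printed lists are the ones programmed and that the optional additions are not used. It does not depend on whether the sub-study safety endpoint is primary, which the SAP leaves uncertain.

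**What to change.** In Appendix 11, item 2, add anaphylactic reaction terms (for example the narrow Anaphylactic reaction SMQ, with its content checked against the MedDRA version used at reporting) and the Type I hypersensitivity preferred term. Apply the revised list to the sub-study and End-of-Study displays. Add a footnote that the definition was updated since earlier cuts, so that differences between reports can be traced. Whether urticaria belongs in the list is for the medical team. If immediate reactions were left out on purpose, the SAP should say so and the AESI should be retitled.

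Separately, state in section 2.2.1 whether the sub-study safety endpoint is primary or secondary, in line with section 7.2.1.

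Completed cuts need not be rerun. The cost is a short edit to a term list, possibly a slightly less favourable hypersensitivity count, and a definition that differs from earlier reports.

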| 
 To assess viral resistance in participants experiencing protocol-defined confirmed virologic failure. To assess patient reported outcomes during the thigh injection phase by administering the following health outcome measurements: Numerical Rating Scale (NRS) and HIVTSQ. | 
 Incidence of treatment emergent genotypic and phenotypic resistance to CAB, RPV during the thigh injection phase. Numerical Rating Scale (NRS): To assess the tolerability of injections during both the Thigh and Gluteal Injection Phase HIVTSQ (both s and c versions): To measure levels of satisfaction and detect change in satisfaction when switching from gluteal to thigh injections in total “treatment satisfaction” score, and individual item scores of the HIV Treatment Satisfaction Questionnaire (HIVTSQ) during the Thigh Injection Phase as well as the change from thigh during the Return to Gluteal Phase. |
| 
 To assess participant's preference of thigh injections during the thigh injection phase compared to gluteal injections. | 
 Preference Questionnaire: To assess patient's preference, and reasons for preference, for injections received during the Thigh Injection Phase compared with prior gluteal injections as well as for injections received during the Return to Gluteal phase compared with prior thigh injections. |
| Exploratory Objectives | Exploratory Endpoints |
| 
 To assess additional safety events including other AEs, SAEs, and safety labs of monthly and every two months dosing of CAB LA and RPV LA following intramuscular injections in the vastus lateral (thigh) muscle in HIV-1 infected participants currently enrolled in the A2M sub-study. | 
 Incidence of other AEs not of special interest, SAEs and change in laboratory and change in laboratory parameters from the last gluteal injection (prior to the Thigh Injection Phase). |

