| Sleep Disorders | CAB+RPV | Clinical, Class, Regulatory Interest, More prevalent in HIV population |

| Adverse Events of Special Interest | Drug(s) of Interest | Reason for Inclusion |
|--|---------------------|---|
| Injection Site Reactions (ISR) from Study Drug Injections [1] | CAB+RPV | Clinical |
| Seizures and Seizure-like Events | CAB | Clinical, Regulatory Interest |
| Weight Gain | CAB | Clinical, Class |
| Rhabdomyolysis | CAB | Clinical, Class |
| Pancreatitis | CAB | Clinical, Therapeutic Area, More prevalent in HIV population |
| Impact on Creatinine | CAB+RPV | Regulatory Interest, Therapeutic Area, More prevalent in HIV population |
| Safety in Pregnancy | CAB | Regulatory Interest, Class |
| Hyperglycaemia | CAB | Class, Regulatory Interest |
| NOTE: [1] A separate analysis will be performed for ISRs from study drug injections as described in Section 8.1.1. | | |

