| Postictal headache | 10052470 |
| Postictal paralysis | 10052469 |
| Postictal psychosis | 10070669 |
| Postictal state | 10048727 |
| Post-traumatic epilepsy | 10036312 |
| Schizencephaly | 10073487 |
| Seizure | 10039906 |
| Seizure anoxic | 10039907 |
| Seizure cluster | 10071350 |
| Seizure like phenomena | 10071048 |
| Severe myoclonic epilepsy of infancy | 10073677 |
| Simple partial seizures | 10040703 |
| Status epilepticus | 10041962 |
| Sudden unexplained death in epilepsy | 10063894 |
| Temporal lobe epilepsy | 10043209 |
| Tonic clonic movements | 10051171 |
| Tonic convulsion | 10043994 |
| Tonic posturing | 10075125 |
| Topectomy | 10073488 |
| Transient epileptic amnesia | 10081728 |
| Tuberous sclerosis complex | 10080584 |
| Uncinate fits | 10045476 |

PTs (Selective)

| PT | PT Code |
|----------------------------------|----------|
| Confusional state | 10010305 |
| Loss of consciousness | 10024855 |
| Syncope | 10042772 |
| Sopor | 10058709 |
| Stupor | 10042264 |
| Altered state of consciousness | 10050093 |
| Depressed level of consciousness | 10012373 |
| Consciousness fluctuating | 10050093 |

14. Weight Gain

HLT General nutritional disorders NEC (Selective)

| PT | PT Code |
|----------------------|----------|
| Abdominal fat apron | 10077983 |
| Overweight | 10033307 |
| Abnormal weight gain | 10000188 |
| Central obesity | 10065941 |
| Obesity | 10029883 |

HLT Physical examination procedures and organ system status (Selective)

| PT | PT Code |
|-------------------------------|----------|
| Weight abnormal | 10056814 |
| Weight increased | 10047899 |
| Waist circumference increased | 10064863 |
| Body mass index abnormal | 10074506 |
| Body mass index increased | 10005897 |

General signs and symptoms NEC (Selective)

| PT | PT Code |
|----------------------|----------|
| Fat tissue increased | 10016251 |

15. Rhabdomyolysis

Rhabdomyolysis/myopathy (SMQ)

| PT | PT Code |
|---------------------------|----------|
| Muscle necrosis | 10028320 |
| Myoglobin blood increased | 10028625 |
| Myoglobin blood present | 10059888 |
| Myoglobin urine present | 10028631 |
| Myoglobinaemia | 10058735 |
| Myoglobinuria | 10028629 |
| Myopathy | 10028641 |
| Myopathy toxic | 10028648 |
| Necrotising myositis | 10074769 |

| PT | PT Code |
|---------------------|----------|
| Rhabdomyolysis | 10039020 |
| Thyrotoxic myopathy | 10081524 |

PTs (Selective)

| PT | PT Code |
|----------|----------|
| Myalgia | 10028411 |
| Myositis | 10028653 |

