
16. Pancreatitis

Acute pancreatitis (SMQ)

| PT | PT Code |
|------------------------------------|----------|
| Cullen's sign | 10059029 |
| Grey Turner's sign | 10075426 |
| Haemorrhagic necrotic pancreatitis | 10076058 |
| Hereditary pancreatitis | 10056976 |
| Ischaemic pancreatitis | 10066127 |
| Oedematous pancreatitis | 10052400 |
| Pancreatic abscess | 10048984 |
| Pancreatic haemorrhage | 10033625 |
| Pancreatic necrosis | 10058096 |
| Pancreatic phlegmon | 10056975 |
| Pancreatic pseudoaneurysm | 10081762 |
| Pancreatic pseudocyst | 10033635 |
| Pancreatic pseudocyst drainage | 10033636 |
| Pancreatitis | 10033645 |
| Pancreatitis acute | 10033647 |
| Pancreatitis haemorrhagic | 10033650 |
| Pancreatitis necrotising | 10033654 |
| Pancreatitis relapsing | 10033657 |
| Pancreatorenal syndrome | 10056277 |

17. Impact on Creatinine

Acute renal failure (SMQ)

| PT | PT Code |
|-----------------------------|----------|
| Acute kidney injury | 10069339 |
| Acute phosphate nephropathy | 10069688 |

| PT | PT Code |
|-------------------------------|----------|
| Anuria | 10002847 |
| Azotaemia | 10003885 |
| Continuous haemodiafiltration | 10066338 |
| Dialysis | 10061105 |
| Foetal renal impairment | 10078987 |
| Haemodialysis | 10018875 |
| Haemofiltration | 10053090 |
| Hyponatriuria | 10077515 |
| Neonatal anuria | 10049778 |
| Nephropathy toxic | 10029155 |
| Oliguria | 10030302 |
| Peritoneal dialysis | 10034660 |
| Prerenal failure | 10072370 |
| Renal failure | 10038435 |
| Renal failure neonatal | 10038447 |
| Renal impairment | 10062237 |
| Renal impairment neonatal | 10049776 |

Renal Failure and Impairment HLT

| PT | PT Code |
|--------------------------------------|----------|
| Acute Kidney injury | 10069339 |
| Anuria | 10002847 |
| Atypical haemolytic uraemic syndrome | 10079840 |
| Cardiorenal syndrome | 10068230 |
| Chronic kidney disease | 10064848 |
| Crush syndrome | 10050702 |
| Diabetic end stage renal disease | 10012660 |
| End stage renal disease | 10077512 |
| Foetal renal impairment | 10078987 |
| Haemolytic uraemic syndrome | 10018932 |
| Hepatorenal failure | 10019845 |
| Hepatorenal syndrome | 10019846 |
| Nail-patella syndrome | 10063431 |
| Neonatal anuria | 10049778 |
| Oliguria | 10030302 |
| Pancreatorenal syndrome | 10056277 |
| Postoperative renal failure | 10056675 |
| Postrenal failure | 10059345 |
| Prerenal failure | 10072370 |

| PT | PT Code |
|----------------------------|----------|

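### The adverse event of special interest named for creatinine is defined by 36 renal terms, none of which is a creatinine, clearance or GFR change

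*SAP*

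**What the plan says.** Table 4 in SAP Section 8.2 names the category and gives its drugs and reasons for inclusion: "Impact on Creatinine | CAB+RPV | Regulatory Interest, Therapeutic Area, More prevalent in HIV population". Appendix 11 (15.11) implements it under "17. Impact on Creatinine" with two lists only, the Acute renal failure SMQ and the Renal Failure and Impairment HLT. The introduction to that appendix says SMQs use narrow terms unless otherwise specified. Item 17 specifies nothing else and has no block of individually selected preferred terms.

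The same introduction leaves room for change: "The additional events may also be added based on the blinded review of AE data collected on study prior to the database freeze". Section 8.2 also says that the list of AESIs may change at reporting.

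AESI membership is used in Section 8.2 for a summary of each category by system organ class and preferred term. It is also used for a table of event characteristics, which in the sub-study is limited to "common AESI which have at least five participants in either treatment arm"; in the main study the threshold is 20 participants in either arm. Section 2.2.1 builds two sub-study endpoints on it: "Incidence and severity of ISRs and AEs of special interest during the thigh injection phase" and "Proportion of participants who discontinue treatment due to ISRs and AEs of special interest during the thigh injection phase". Events outside the AESI lists go to an exploratory sub-study endpoint: "Incidence of other AEs not of special interest, SAEs and change in laboratory".

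**The concern.** The heading and the rule do not agree. A reader of a table titled for creatinine expects to find reported creatinine events in it. As the list is printed, an event coded only as a creatinine rise, or only as a fall in clearance or GFR, is not flagged. An empty or sparse table could be read as meaning that no such events were reported.

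The plan does list the measurement term for another category named for a measurement. Item 14, Weight Gain, includes "Weight increased | 10047899". Items 2, 3, 4, 13 and 15 supplement their queries with selected preferred terms. Item 17 does neither.

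The consequence is greatest in the sub-study. Two of its endpoints count AESIs, while other events are exploratory only. A creatinine-only event, including one that led to discontinuation, would therefore be classed as exploratory solely because of the term list.

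**Working it through.** The plan states no figure to reproduce here. The check is a count of the printed terms and of what depends on them.

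**Step 1: count the terms in item 17 (SAP 15.11).**

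- Acute renal failure SMQ: 19 preferred terms.
- Renal Failure and Impairment HLT: 27 preferred terms.
- Shared by code: acute kidney injury, anuria, foetal renal impairment, neonatal anuria, oliguria, prerenal failure, renal failure, renal failure neonatal, renal impairment, renal impairment neonatal. That is 10.
- Distinct terms: 19 + 27 − 10 = 36.

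**Step 2: search the 36 for the concept in the heading.** Terms naming creatinine, clearance, filtration rate or GFR: 0 of 36. The nearest is azotaemia, which is a different preferred term. The 36 cover renal failure, impairment and injury, reduced urine output, dialysis-type procedures and related syndromes.

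**Step 3: see whether another category catches the event.** No other printed term list in the appendix contains a creatinine, clearance or GFR change. Item 18, Safety in Pregnancy, has no term list; it takes whatever is co-reported with a pregnancy exposure, so it could catch such an event only in that setting.

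**Step 4: put the thresholds on the scale of the arms.**

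- Main study: 1020 randomized 1:1 (SAP 2.3) gives about 1020 / 2 = 510 per arm. The trigger of 20 participants is 20 / 510 = 3.9%.
- Sub-study: about 41 per arm (SAP 2.3). The trigger of 5 participants is 5 / 41 = 12.2%.

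Creatinine-only events add nothing to either count.

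**Step 5: size of the omission.** The SAP gives no number of such events. Assuming 1 to 3 affected participants in one sub-study arm, the share left out of this category's incidence is 1 / 41 = 2.4 to 3 / 41 = 7.3 percentage points. If no such event occurs, nothing is left out.

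**The case against.** The strongest reply is that item 17 follows a pattern. Item 1 (hepatotoxicity) lists no transaminase or bilirubin increase, item 16 (pancreatitis) no lipase or amylase increase, and item 15 (rhabdomyolysis) no creatine kinase increase. On this view clinical events belong to the AESI, measured changes belong to the laboratory displays, and only the label is loose. That holds only in part. Items 4, 14, 15 and 19 do print measurement-type terms: electrocardiogram QT prolonged, weight increased, myoglobin blood increased and blood glucose increased. Items 1, 15 and 16 are titled for a clinical condition, whereas item 17 is titled for the analyte.

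Second, creatinine is analysed elsewhere, and from measured values. GFR is estimated from creatinine and from cystatin C (15.6.4), and chemistry changes and graded toxicities are tabulated for the main study and the sub-study (15.15.5.4, 15.15.7.4). The adverse event itself stays in the all-event, drug-related and withdrawal tables and in the listings. Withdrawal under renal toxicity criteria is recognised in the Snapshot and time-to-event rules (15.9, 15.10). All of this stands and limits the harm: the information is not lost. It does not put the event into the AESI outputs or the sub-study AESI endpoints.

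Third, the plan allows terms to be added. It does, but only as an option, and it names no creatinine term.

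Fourth, the number of affected participants is unsupported by the document, and 1 to 3 would not by themselves reach the five-participant trigger. Both points are right. The outputs are descriptive, and the understatement arises only if such an event occurs.

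**Conclusion.** The concern holds. Followed exactly, item 17 leaves an adverse event coded only to a creatinine, clearance or GFR change out of the category named for creatinine, and so out of the two sub-study AESI endpoints. The term count is exact: 0 of 36. The 2.4 to 7.3 percentage points rest on an assumed 1 to 3 participants in an arm of about 41. No difference between arms and no effect on the primary analysis or any hypothesis test is claimed. This should be corrected, but it does not threaten the trial's main conclusions. Confidence is medium, because the sponsor may have meant a renal-event category or may intend to use the option to add terms.

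**What to change.** Add a block of selected preferred terms to item 17, in the format already used in items 2, 3, 4, 13 and 15. It should contain the creatinine-increased, creatinine-clearance-decreased and GFR-decreased terms of the MedDRA version in use. Apply it to the sub-study and End-of-Study AESI outputs.

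If only renal failure and impairment are meant, renaming the category would remove the mismatch, but it would leave creatinine-only events outside the AESI endpoints.

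The cost is one table edit in the SAP and a wider flag in the adverse event dataset. Counts for this category may rise and would no longer be directly comparable with the earlier data cuts, so either footnote the change or re-run those outputs.
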